3. OBJECTIVES AND ENDPOINTS

Primary Objective	Primary Endpoint
To assess safety and tolerability of CX-4945 administered orally twice daily to patients with severe COVID-19	• Adverse Events experienced by patients from randomization to Day 60 (including vital signs, physical findings, clinical laboratory, and ECG results) as characterized by type, frequency, severity (as graded by Common Terminology Criteria for Adverse Events (CTCAE version 5.0), timing, seriousness, and relationship to study therapy.
Secondary Objectives	Secondary Endpoints
• To compare time to clinical recovery in the CX-4945 treatment group evaluated from randomization through Day 28 as compared to the control arm.	• Number of days from randomization to discharge, or alleviation of cough (defined as mild or absent in a patient reported scale of 0=absent, 1=mild, 2=moderate, and 3=severe). Improvement must be sustained for at least 48 hours.
	• Number of days from randomization to normalization of fever (defined as <36.6°C from axillary site, or < 37.2°C from oral site or < 37.8°C from rectal or tympanic site), normalization of respiratory rate (< 24 bpm while breathing room air), resolution of hypoxia (defined as SpO2 ≥ 93% in room air or P/F ≥ 300 mmHg). All these improvements must be sustained for at least 48 hours.
	 Number of days from randomization to the first day on which the subject satisfies one of the following three categories from the ordinal NIAID 8-point Clinical Progression Outcomes scale collected daily from randomization through Day 28:
	Hospitalized, not requiring supplemental oxygen - no longer requires ongoing medical care;
	 Not hospitalized, limitation on activities and/or requiring home oxygen;
	Not hospitalized, no limitations on activities.
To compare changes in clinical status of patients enrolled to CX-4945 treatment arm as	Difference in percentage of subjects with clinical recovery compared at Day 14 and Day 28. Clinical recovery is defined as:

CONFIDENTIAL Page 22 of 66

s. ty	ite, or < 37.2°C from oral site or < 37.8°C from rectal or ympanic site), normalization of respiratory rate (< 24 bpm
a	while breathing room air), resolution of hypoxia (defined as $SpO2 \ge 93\%$ in room air or $P/F \ge 300$ mmHg). All these mprovements must be sustained for at least 48 hours.
Day	centage of participants at each clinical status at Day 14 and 28 assessed by using the ordinal NIAID 8- point Clinical gression Outcomes scale:
1) L	Death;

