4. STUDY DESIGN

4.1. OVERALL DESIGN

This is a phase II multi-center, randomized, open-label, 2 arm parallel-group controlled interventional prospective study of CX-4945 in patients with severe COVID-19. Up to approximately 40 patients will be enrolled into this study. A screening evaluation will occur within 7 days prior to Day 1. All qualified patients will be randomized at Day 1 in a ratio of 1:1 to one of the following two treatment arms:

- Arm A: SOC*/ best supportive care** in combination with CX-4945 1000 mg BID PO or
- Arm B: SOC*/ best supportive care** alone
- * The standard of care (SOC) is not pre-specified, may vary among patients, and may include agents with anti-viral activity, such as remdesivir, among others. Investigator discretion is to be applied for any established SOC. Active concomitant treatment with other investigational antivirals or immunomodulators are not permitted
- ** Best supportive care is defined as intensive care therapy according to current guidelines, evidence, and best practice, including but not limited to lung protective ventilation, thrombosis prophylaxis, renal replacement therapy when indicated, and access to advanced therapies including extracorporeal membrane oxygenation.

The total duration of the treatment will be 14 days. Patients will be followed up at 28, 45 and 60 days from the start of the treatment. The total duration for each patient in the study (including the screening) will be up to 67 days. For details on randomization see Randomization in **Section 6.1.2.**

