6.1.3. Dosing and Administration of CX-4945

Patients enrolled to the treatment Arm A will receive 1000 mg of CX-4945 twice daily by mouth, beginning on Day 1, and continuously through Day 14.

Patients will be instructed to take oral antiemetic prophylaxis at least 1 hour prior to taking the study drug. Other oral medications should be taken at least one hour before or 2 hours after ingesting the dose of CX-4945 capsules.

CONFIDENTIAL Page 30 of 66

^{*}SOC and Supportive Care are defined in Section 4.1.

Patients will take five 200-mg CX-4945 capsules twice daily, two hours after the morning meal and two hours after the evening meal (dinner) with water. Patients are advised to take 1 capsule at a time with a pause in between each. This method may prevent a clumping effected in the stomach, so patient can take as much as 10 minutes to swallow each capsule.

The study drug will be taken on an empty stomach with at least six ounces (180 mL) of water. After CX-4945 administration, the patient will be NPO (except for water) for 2 hours, after which, the patient may eat.

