8.2.1.2. Adverse Events

CONFIDENTIAL Page 39 of 66

Assessment of adverse events will include the type, incidence, severity (graded by the CTCAE version 5.0) timing, seriousness, and relatedness. For AE assessment details, see **Section 8.3.3**. Investigator will follow-up for any AEs/SAEs and mortality status at Day 28, Day 45 and Day 60.

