8.3.4. Reporting of Adverse Events

Report initiation for all AEs and SAEs will begin at the time of randomization and continue until the end of final study visit. All events will be followed to resolution or until the subject completes the study. A final assessment of outcome will be made at that time.

All AEs must be recorded in the subject's study records. AEs will be reported using customary medical terminology along with the following information: the onset and end dates, whether the event is considered to be a SAE (see Section 8.3.2), the impact the event had on study treatment (see Section 8.3.4.1), the Common Terminology Criteria for Adverse Events (CTCAE) grade (intensity) of the event (see Section 8.3.3.1), the causality of the event (see Section 8.3.3.2), whether treatment was given as a result of the event (see Section 8.3.4.2), and the outcome of the event. (see Section 8.3.4.3)

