9.8.4.3. Safety Summaries

Adverse Events

Adverse events will be coded using the most recent version of Medical Dictionary for Regulatory Activities (MedDRA). Treatment Emergent AE's (TEAE) are defined as events with an onset on or after the first treatment. TEAEs will be summarized by treatment group, System Organ Class, and preferred term. The following TEAE summaries will be provided:

- Overall (i.e., regardless of severity or relationship to treatment);
- By intensity (mild, moderate, severe, life threatening or death);
- By causality (definitely, probably, possibly, remotely or unrelated);
- By impact on study treatment (dose increased, dose not changed, dose rate reduced, dose reduced, drug interrupted, drug withdrawn, not applicable, or unknown).

In addition, separate summaries of serious adverse events, and adverse events resulting in discontinuation of study treatment will be presented.

Clinical Laboratory Data

All laboratory values will be listed. Laboratory measurements will also be summarized and presented by treatment group and time point.

CONFIDENTIAL Page 52 of 66

ECG

All ECG values will be listed. ECG measurements will also be summarized and presented by treatment group and time point.

Vital Signs

All vital sign findings will be listed and/or summarized.

Physical Examination

All physical examination findings will be listed and/or summarized.

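### Adverse-event timing is part of the primary endpoint, but Section 9.8.4.3 lists no onset-time or period summary, so its main AE tables pool up to 14 on-drug days with 46 off-drug days

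*Combined protocol and SAP*

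**What the plan says.** Section 3 defines the primary endpoint as "Adverse Events experienced by patients from randomization to Day 60", described by type, frequency, severity, "timing, seriousness, and relationship to study therapy". Section 8.2.1.2 repeats the list: "Assessment of adverse events will include the type, incidence, severity (graded by the CTCAE version 5.0) timing, seriousness, and relatedness".

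Section 6.1.3 has Arm A dosed "beginning on Day 1, and continuously through Day 14". Section 4.1 adds "Patients will be followed up at 28, 45 and 60 days from the start of the treatment". On collection, Section 8.3.4 states "Report initiation for all AEs and SAEs will begin at the time of randomization and continue until the end of final study visit", and it requires onset and end dates for each event.

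Section 9.8.4.3 defines a treatment-emergent AE (TEAE) by onset at or after first treatment and gives no closing day. It then says "TEAEs will be summarized by treatment group, System Organ Class, and preferred term". The listed tables are: overall, by intensity, by causality, by impact on study treatment, serious AEs, and AEs that led to stopping study treatment. Laboratory and ECG data are to be shown by arm and time point; AEs are not. The Kaplan-Meier and Cox methods in Section 9.8.4.1 are given for efficacy.

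**The concern.** Safety and tolerability is the primary objective, and with 20 patients per arm and no inference planned (Section 9.8.4) the by-arm AE tables are essentially the whole safety result. Severity, seriousness and relationship each have a table. Timing has none.

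The toxicity the protocol describes is early: Section 6.3.2 puts the median onset of the later form of diarrhoea at 2 days. The patients are in hospital with severe COVID-19, so complications unrelated to CX-4945 can plausibly arise in both arms after dosing ends. A table that counts everything to Day 60 adds those events to both arms. The arm difference in patients affected can then shrink, and a short-lived drug effect can look like background.

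**Working it through.** **Which listed summary uses time**

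| Endpoint feature (Section 3) | AE summary in Section 9.8.4.3 |
|---|---|
| Type, frequency | By arm, organ class and preferred term; overall |
| Severity | By intensity |
| Seriousness | Serious AE summary |
| Relationship | By causality |
| Timing | None listed |

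**The window.** The plan's own duration figure reproduces: 7 days of screening + 60 days = 67 days. Off-drug days are 60 − 14 = 46, and 46/60 = 77% of the AE window.

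**Size of the dilution.** The documents give no AE rates, so every risk below is an assumption. Only the 20 per arm (40 patients randomised 1:1, Section 9.3) and the 14-day and 60-day windows come from the plan.

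Let p14 and p60 be the control risks of at least one event of a given kind by Day 14 and Day 60. Let CX-4945 multiply the hazard by m on Days 1-14 only. Then

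- Arm A by Day 14 = 1 − (1 − p14)^m
- Arm A by Day 60 = 1 − (1 − p14)^m × (1 − p60)/(1 − p14)

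The chance of no excess is P(Arm A count ≤ Arm B count) for two independent binomials with n = 20.

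*Constant background, p60 = 50%, m = 2.5.* The daily hazard is −ln(0.5)/60 = 0.01155, so p14 = 1 − exp(−14 × 0.01155) = 14.9%.

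- Days 1-14: 33.3% v 14.9%, difference 18 points, ratio 2.2, chance of no excess 11%.
- To Day 60: 60.8% v 50%, difference 11 points, ratio 1.2, chance of no excess 30%.
- With p60 from 40% to 60% and m from 2 to 3, the ratio falls from 1.8-2.7 to 1.1-1.3.

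*Front-loaded background, p60 = 50%, m = 2.5, p14 = 35%.*

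- Days 1-14: 1 − 0.65^2.5 = 65.9% v 35%, difference 31 points, chance of no excess 3%.
- To Day 60: 1 − 0.341 × 0.50/0.65 = 73.8% v 50%, difference 24 points, chance of no excess 8%.
- With p14 = 45%, the chance of no excess rises only from 2% to 3%.

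**A second model.** Let the drug add an independent risk q on Days 1-14. The arm difference is then q × (1 − control risk). With q = 0.30 and constant background:

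| Control risk by Day 14 | Control risk by Day 60 | Difference, Days 1-14 | Difference to Day 60 |
|---|---|---|---|
| 0% | 0% | 30.0 points | 30.0 points |
| 10% | 36.3% | 0.30 × 0.90 = 27.0 | 0.30 × 0.637 = 19.1 |
| 20% | 61.6% | 0.30 × 0.80 = 24.0 | 0.30 × 0.384 = 11.5 |

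If background is 10% by Day 14 with only a further 10% risk afterwards, and q = 0.40, the difference falls from 36.0 to 32.4 points.

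Both models agree. Pooling weakens the contrast when the same kind of event goes on occurring after Day 14. The loss is large if background is steady, small if it is front-loaded, and nil if there is none.

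**The case against.** Four objections have weight.

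1. **Some tables already separate on-drug events.** Dosing ends by Day 14, so the discontinuation table is close to an on-drug table. The impact table reserves its not-applicable code for events after the Treatment Phase (Section 8.3.4.1). The causality table isolates events attributed to the drug, with temporal sequence as a criterion. This stands, so it would be wrong to say that every AE table mixes the periods. None of these replaces a by-arm comparison over the same days, however. Arm B has no study drug to stop, the use of the not-applicable code in Arm B is unclear, and causality is an investigator's judgment in an open-label trial.

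2. **Known toxicities may be barely diluted.** A reader might infer that pooling hides any CX-4945 toxicity. The documents do not support that. The main table is by preferred term, the expected events are nausea, vomiting and diarrhoea, and a term with little background after Day 14 keeps its contrast.

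3. **Detail is deferred.** A reader might also infer that timing will never be analysed. Sections 9 and 9.8 leave detailed methods to a separate SAP, to be approved before database lock, whose text is not in the documents supplied. Onset dates are recorded and all data will be listed (Section 9.7). The supportable statement is that this document does not specify a timing summary. A listing is still not a by-arm summary, and Section 9.8.4.3 already enumerates the AE tables.

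4. **The study is exploratory.** Its size was set by clinical judgment and no inference is planned. No test or decision rule fails, and the data can be re-tabulated later. The harm is to descriptive interpretation. If the periods are chosen after open-label data have been seen, though, the choice is open to question.

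**Conclusion.** The point holds in a limited form. A named feature of the primary endpoint has no corresponding AE summary in Section 9.8.4.3, and the open-ended TEAE definition makes the overall, intensity and serious-event tables run through 46 off-drug days. For event types with background after Day 14, this can dilute the by-arm contrast for an early, transient toxicity.

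The rise from 11% to 30% should not be read as the expected loss. It rests on a constant background hazard, which the documents neither state nor support, and patients who enroll while acutely ill may well have most of their events early. The front-loaded case gives 3% to 8%. The direction is firm wherever later background exists; the size is not known. Severity: should fix.

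**What to change.** In Section 9.8.4.3, or in the SAP before database lock:

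- Keep the Day 60 tables.
- Add by-arm tables of all AEs, Grade 3 or higher AEs and serious AEs by onset period: Days 1-14 plus a lag that the sponsor prespecifies, then follow-up to Day 60. Show the number of patients at risk in each period.
- Count from randomisation/Day 1 in both arms. First treatment, the present TEAE anchor, has no study-drug meaning in Arm B.
- Add onset day, or time to first AE, by arm.
- Exact intervals for each arm and for the difference are optional, because the plan is descriptive.

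The cost is SAP wording and a few more tables, some with small counts. The follow-up table describes only patients still at risk, so it is a less clean randomised comparison than the first period and should be labelled as such. No new data and no more patients are needed, since Section 8.3.4 already requires onset dates.

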8.2.1.4. Laboratory Safety Assessment

Hematology and blood chemistry will be drawn at the time points described in the Schedule of Activities (see **Section 1.3**) and analyzed at local laboratories. Unscheduled clinical labs may be obtained at any time during the study to assess any perceived safety concerns. Samples for hematology, blood chemistry, coagulation, pregnancy and urinalysis will be analyzed by the site's local laboratory.

Table 4. Safety Laboratory Tests

Hematology	Chemistry	Coagulation	Urinalysis	Pregnancy Test
Hemoglobin	ALT	PT or INR	color, appearance, specific gravity, pH, protein, glucose, occult blood, ketones, leukocyte esterase, nitrite, bilirubin, urobilinogen	For female patients of childbearing potential, serum or urine
Hematocrit	AST			
RBC	Alk Phos			
Platelets	LDH			
WBC	Total Protein			
Absolute Neutrophils	Sodium			

CONFIDENTIAL Page 40 of 66

Hematology	Chemistry	Coagulation	Urinalysis	Pregnancy Test
Absolute Lymphocytes	Potassium		microscopic examination of urine sediment	
Absolute Monocytes	Ferritin			
Absolute Eosinophils	Chloride			
Absolute Basophils	Calcium			
	Bicarbonate			
	Total bilirubin			
	d-dimer			
	Creatine (serum)			
	BUN			
	Albumin			
	C-reactive Protein (CRP)			
	Creatinine Clearance			
	IL-6			
	Creatine Phosphokinase (CPK)			
	eGFR			

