8.3.1. Definitions of Adverse Event (AE)

An adverse event (AE) is defined as any unfavorable or unintended sign, symptom, or disease that occurs or is reported by the patient to have occurred, or a worsening of a pre-existing condition. An adverse event may or may not be related to the study treatment.

AEs will be elicited through direct questioning and subject reports. Any abnormality in physical examination findings or laboratory results that the investigator believes is clinically significant (CS) to the research subject and that occurred after initiation of the first study treatment will be reported as AEs. Abnormal findings that are NOT clinically significant should not be recorded as an AE.

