9.7. GENERAL STATISTICAL CONSIDERATIONS

All collected study data will be presented in subject data listings. Descriptive statistics (n, mean, standard deviation, median, minimum and maximum) will be presented by treatment group for continuous variables. Frequencies and percentages will be presented by treatment group for categorical variables.

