9.9. DMC PERIODIC SAFETY REVIEW

An independent Data Monitoring Committee (DMC) established by the site will be used during the study to ensure subject safety and trial integriry and also to provide support in assessment of any new possible safety risks imposed by the COVID-19 public health emergency on patient safety and its possible impact of protocol implementation.

The DMC will review the listings of adverse events, protocol deviations, and an enrollment summary. The first formal safety review will occur after the first 3 patients randomized to the CX4945 treatment (Arm A) complete their treatment course. The study accrual will not be interrupted for the scheduled safety reviews, if no specific study-related safety concerns are raised by the Sponsor-Investigator of DMC members. Subsequent periodic safety review will be scheduled as prespecified in the DMC charter. The DMC or Sponsor-Investigator may request an ad hoc meeting for any reason, including a significant unexpected safety event, follow-up of observations during a planned DMC meeting, high enrollemnt rate, or a report external to the study, such as publication of study results from a competing product. The DMC will communicate major safety concerns and recommendations regarding study modification or termination to Sponsor-Investigator. Recommendations are not legally binding but require consideration and a formal written response from the Sponsor-Investigator. Further details are provided in the DMC charter.

CONFIDENTIAL Page 53 of 66

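### The protocol specifies no by-arm table of graded, worst or baseline-shift laboratory results and names no laboratory data for the DMC

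*Combined protocol and SAP*

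**What the plan says.** The primary endpoint (Section 3) is adverse events to Day 60, "including vital signs, physical findings, clinical laboratory, and ECG results", described by frequency and CTCAE severity among other features. Section 9.2.1 separately lists changes in chemistry, including electrolytes, in hematology and coagulation, and in ECG as safety measures.

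Three passages govern how a laboratory value reaches a reader:

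- **Report.** Section 9.8.4.3 states "All laboratory values will be listed" and then "Laboratory measurements will also be summarized and presented by treatment group and time point". ECG is handled the same way. Section 9.7 defines the content: "Descriptive statistics (n, mean, standard deviation, median, minimum and maximum) will be presented by treatment group for continuous variables".
- **AE tables.** These are by arm and by intensity, but Section 8.3.1 instructs that "Abnormal findings that are NOT clinically significant should not be recorded as an AE". Section 9.5 makes the trial open label.
- **DMC.** Section 9.9 states "The DMC will review the listings of adverse events, protocol deviations, and an enrollment summary". Further detail is left to a charter.

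Section 8.2.1.4 adds that "Unscheduled clinical labs may be obtained at any time during the study to assess any perceived safety concerns". No rule assigns such values to a time point in the summaries. Section 6.3.3 describes electrolyte abnormalities as common with CX-4945 and as a possible route to arrhythmia.

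**The concern.** The control arm lets the reader judge whether toxicity exceeds the background of severe COVID-19. For laboratory toxicity the useful quantity is the number of patients per arm who reached a severe grade after baseline, set against where they started. The only graded by-arm tables named are the AE tables, and entry to those passes through a judgement made with the arm known. That judgement can differ between arms, in either direction. The tables that do not depend on it are descriptive statistics by visit, which contain no grades and do not count patients.

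The DMC has the same limitation. On the protocol text it sees laboratory toxicity only where an abnormality was recorded as an AE, although the protocol itself flags electrolytes as a known risk of this drug. At stake is whether an excess of severe electrolyte, liver or renal values in Arm A would be apparent to the DMC during the trial, and in a by-arm table at the end.

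**Working it through.** The plan has no figure to reproduce. Section 9.3 gives no power calculation, and Section 9.8.4 plans no inferential statistics for study outcomes.

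**Inputs.** 40 patients randomized 1:1 (Section 9.3), so 40/2 = 20 per arm. Laboratory draws at Screening and Days 1, 4, 8, 11, 14, 28 and 45 (Section 1.3), of which Days 4, 8, 11 and 14 are on treatment after baseline. ECG at Screening and Day 14 only (Sections 1.3 and 8.2.1.5).

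**Step 1: trace each kind of abnormal value through the named outputs.**

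| Value | Judged clinically significant? | By-arm AE tables | By-arm visit summary | Listing | Named DMC package |
|---|---|---|---|---|---|
| Scheduled | Yes | Yes | Yes | Yes | As an AE |
| Scheduled | No | No | Yes, ungraded | Yes | No |
| Unscheduled | Yes | Yes | No rule | Yes | As an AE |
| Unscheduled | No | No | No rule | Yes | No |

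Only the last row has no assured place in any by-arm table. The second row is in a by-arm table, but one without grades or patient counts.

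**Step 2: patients counted once versus counted by visit (assumed inputs).** Suppose k of 20 Arm A patients each have one Grade 3 or higher value, spread evenly over the four on-treatment draws.

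- Worst-grade proportion = k/20.
- Average per-visit proportion = (k/4)/20.
- k = 4: 4/20 = 20% against 1/20 = 5%.
- k = 2: 2/20 = 10% against 0.5/20 = 2.5%.
- k = 8: 8/20 = 40% against 2/20 = 10%.

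The reverse ambiguity also holds. One affected patient at each of four draws could be the same patient throughout (1/20 = 5%) or four different patients (4/20 = 20%). The planned minimum and maximum give one extreme per visit and cannot separate these cases. Nor would the planned summary print the 5%, because it does not grade values.

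**Step 3: baseline.** Section 5.1.1 admits AST and ALT up to 2.5 times ULN and albumin down to 2.5 g/dL. A post-baseline extreme in a visit summary therefore does not by itself show a change on treatment. A shift from the patient's own baseline does.

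**The case against.** The strongest reply is that little is lost. Every laboratory value is listed, and Section 9.7 extends listing to all collected data. A scheduled extreme is visible by arm in the minimum or maximum, whatever the investigator thought of it. A between-visit value judged clinically significant is an AE and is counted by arm and intensity. With 40 patients, listings can be read through. All of this stands. A reader might infer that toxic values vanish from the report, or that any between-visit or non-significant value drops out of the comparison; the documents support neither. What survives is narrower: a listing or a per-visit extreme is not a count of affected patients by arm.

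A reader might also measure the problem by the chance that a short excursion falls between scheduled draws. That would be the wrong measure. A value never drawn cannot be recovered by any table, and one drawn between visits is listed.

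The endpoint can fairly be read as AEs, with laboratory and ECG results as a source of them; the graded AE tables then answer it. But Section 9.2.1 makes laboratory change a safety measure in its own right.

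Knowledge of the arm need not suppress reports in Arm A. The electrolyte warning in Section 6.3.3, and Table 3's link from attributed grade to treatment modification, could raise them. The direction is unknown, which is itself a reason for counts that do not depend on the judgement.

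Finally, Section 9 defers detail to a separate SAP, and Section 9.9 to a charter. Neither is available here and either may already contain these tables. That limits the claim to what the protocol specifies. However, Section 9.8.4.3 does enumerate the safety outputs, and the SAP need only be approved before database lock (Section 9.8), which in an open-label trial may be after results have been seen.

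**Conclusion.** The point holds in a limited form. As written, the protocol specifies no by-arm table of CTCAE-graded, worst post-baseline or baseline-shift laboratory results and names no laboratory data for the DMC. Abnormalities not judged clinically significant are absent from the graded AE counts. At scheduled visits they appear only in by-visit statistics and listings; unscheduled ones appear only in listings, unless the SAP assigns them to a time point.

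The size can only be illustrated: 20% against 5% per visit for four affected patients in 20, and 10% to 40% against 2.5% to 10% for two to eight. This assumes one severe value per affected patient, an even spread over four draws and complete data. The documents give no rate of severe values and no rate at which they would be judged not significant, so the actual loss cannot be estimated.

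This is a cheap improvement rather than an error in the plan. It is worth making because safety is the primary objective and, with no inferential statistics planned for outcomes in Section 9.8.4, the descriptive tables carry the comparison.

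**What to change.** **Section 9.8.4.3 and the SAP.** For each laboratory parameter that CTCAE grades, add a by-arm shift table from the last value on or before Day 1 (before first dose in Arm A) to the worst post-baseline grade. Use scheduled and unscheduled values, whether or not they were judged clinically significant. Add a version restricted to scheduled values, since unscheduled testing may differ by arm. For ECG, show the shift from the last pre-treatment recording, normally Screening because no Day 1 ECG is scheduled, to Day 14 and any unscheduled recording.

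**Section 9.9 and the DMC charter.** Add these by-arm laboratory tables, with denominators, to the DMC package. At the first review, which follows only three completed Arm A courses, graded laboratory listings would serve instead.

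**Cost.** A few programmed tables and some SAP and charter wording. The values are already collected and listed, so no new tests are needed. The main downside is that unequal unscheduled testing could distort the all-values table, which the scheduled-only version is there to reveal.
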